Spinal Cord Injury Program in Exercise (SCIPE)

NCT03925077

Study Protocol

July 22nd, 2023

Checklist for SCiPE Participant Screening to Enrollment

Once a potential participant completes the SCiPE study *F01 Pre-screening Form (F01 Form, Application)* through the screening website, the pre-screening data will be automatically fetched to an inactive arm (Arm 2) of the study database (REDCap SCiPE) if the potential participant is eligible based on the **age** and **SCI diagnosis criteria**. **If a potential participant made a wrong entry in the *F01 Form* and was rejected to be part of the study, See Appendix II.**

Screening website - <https://screen.scipe.org/#/apply>

REDCap link- <https://redcap.dom.uab.edu/index.php?action=myprojects>

All data fetched to the Arm 2 will go through automatic duplicate checks to ensure that each individual has only one study ID. The duplicate check is performed based on the following rules: **Name** (first and last) and **Phone Number**. IDs that are identified as duplicates will remain in the Arm 2. Non-duplicate IDs and associated data will be transferred to active arm (Arm 1) in REDCap. All data moved to the Arm 1 will be automatically saved. This fetching, duplication check, and the saving process happen daily at a scheduled time (every 30 min) using a computer-generated script.

Once an ID with the fetched data is automatically saved under *F01 Form* in REDCap (status remains as incomplete, RED), it will trigger an automatic survey invitation and sent out *F02 Screening Interview Form (F02 Form)* to that individual. The *F02 Form* includes question items to obtain personal information, PAR-Q+, and secondary contact information. **We can manually check whether or not the invitation was sent in two places (See Appendix III).**

Recruitment Coordinator should check the study database daily to:

- 1) Ensure that data is fetched to REDCap (Step 1);
- 2) Monitor completion of the *F02 Form* (Step 2 – 6);
- 3) Identify individuals who need medical clearance, obtain one when necessary, and ensure individuals' mailing addresses (Step 7 – 11); and
- 4) Monitor completion of the consenting process (Step 12 – 17).

Please check each step below to complete the screening to enrollment process.

Please ensure all phone calls are documented using the *Call Log* in REDCap.

Step	✓	Description

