If the participant did not respond to the phone call, please make 2 additional call attempts, with each 3 days apart. Enter the **date** when the 2nd or 3rd call attempt is made under the *Post-Intervention Participant Interview* form in REDCap.

If participant answers the call, follow **Action #1-3** to complete the interview process.

If participant still did not respond to the 3rd call attempt, please **Save and Exit** the form as **Incomplete**. This action will remove the participant from the *Participants to be Invited for Interview* report.

Statistical Analysis for Pilot Usability Phase

Descriptive statistics for participant demographics, feasibility, usability, acceptability metrics, and preliminary study outcomes were computed as mean \pm SD or median (minimum, maximum) for continuous variables and percentage (*n*) for categorical variables. A sample size of 36 was determined based on recommendations for feasibility studies assessing feasibility, usability, and acceptability³⁸.

Preliminary data (LTPAQ-SCI and PROMIS) collected at baseline and Week 8 were analyzed, with Week 8 as the primary endpoint. Prior to analyses, data were examined for errors, missingness, and normality. Three participants (*n*=1 in SET, *n*=2 in AC) were identified as outliers for all LTPAQ-SCI categories (Studentized residual > 3.0 and high leverage on predictors of interest). These data were presumed to result from measurement errors and were excluded from all LTPAQ-SCI analyses.

Given the exploratory nature of this interim analysis and the small sample size, we focused on effect sizes for the preliminary study outcomes. Linear mixed models were used to assess within- and between-group effects using an intent-to-treat approach and included fixed effects for Time (Week 8 vs baseline) and Intervention Arm, a random effect for participant, and a Time x Intervention Arm interaction. Estimates were derived from least-square mean differences, with bootstrap confidence intervals (CIs) calculated at the 95%, 85%, and 75%. All LTPAQ-SCI measures were square-root transformed for analysis to meet normality assumption.

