Effect sizes were calculated using Hedge's *g*, which is based on the pooled SD and corrected for small samples. Interpretations of *g* were: $g < 0.2$ =very small; $0.2 \leq g < 0.5$ =small; $0.5 \leq g < 0.8$ =medium; $g \geq 0.8$ =large³⁹. Rank-biserial correlation index (*r_{rb}*) were also used with the following interpretations: $0.05 \leq r_{rb} < 0.1$ =very small; $0.1 \leq r_{rb} < 0.2$ =small; $0.2 \leq r_{rb} < 0.3$ =medium; $0.3 \leq r_{rb} < 0.4$ =large; $r_{rb} \geq 0.4$ =very large⁴⁰.

Analyses were performed using R version 4.3.3 (R Core Team, 2024)⁴¹ and the following packages: tidyverse v2.0.0⁴², DescTools v0.99.54⁴³, gtsummary v1.72⁴⁴, lme4 v1.1-35.3⁴⁵, lmerTest v3.1-3⁴⁶, emmeans v1.11.0⁴⁷, effectsize v0.8.7⁴⁸, broom.mixed v0.2.9.6⁴⁹, ggplot2 v3.5.2⁵⁰, and ggpubr v0.6.0⁵¹.

Statistical Analysis for Feasibility Phase

Data collected at baseline and Week 8 were included in the current analyses, with Week 8 evaluated as the primary endpoint. The primary outcome for this study was change in physical activity (LTPAQ-SCI), whereas changes in physical, mental and social health (NIH PROMIS) were evaluated as secondary outcomes. All data were examined prior to analysis for errors, missingness, and normality. For LTPAQ-SCI measures, five participants ($n=3$ in Arm 1 and $n=2$ in Arm 2) had unusually high scores for mild, moderate, and total LTPA, and were identified as model outliers for these outcomes (Studentized residual > 3.0 and high leverage). Ultimately, these participants were excluded from analyses of the primary outcome due to the high likelihood of data entry errors during data collection.

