Descriptive statistics were computed as mean (SD) and median (min, max) for continuous variables, and n (%) for categorical variables. Characteristics for the overall sample and by intervention arm were reported for 1) demographics, spinal cord injury, health, and lifestyle at baseline; and 2) primary and secondary outcomes at baseline and Week 8. Additionally, results for exercise enjoyment (PACES) were reported for Arm 2 participants at Week 8. Group differences in descriptive characteristics were assessed with the Wilcoxon rank-sum test (non-parametric two-sample t-test), Pearson's Chi-squared test, or Fisher's exact test as appropriate. Mixed models were used to evaluate within- and between-group effects on the primary and secondary outcomes, with analyses conducted using an intent-to-treat approach. Models included time (baseline vs Week 8) and intervention (Arm 1 vs Arm 2) as fixed effects, participant as a random effect, and an interaction term for time x intervention arm. Within- and between-group estimates were derived from the interaction term and are reported as the difference in least-square means (95% CI). For these analyses, all LTPAQ-SCI measures were square-root transformed to ensure that the normality assumption was met, and confidence intervals were estimated via bootstrap methods. All analyses were performed using R version 4.5.0 (R Development Core Team, 2025) (3) and the following packages: tidyverse (4), doBy (5), broom.mixed (6), DescTools (7), gtsummary (8), lme4 (9), lmerTest (10), emmeans (11), effectsize (12), psych (13), and ggplot2 (14). Significance was set at $\alpha=0.05$ for all analyses.

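### The Feasibility-phase analysis section reports finished work, including primary-outcome exclusions made with the data in hand, so its 0.05 significance level is not assured for LTPAQ-SCI

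*Combined protocol and SAP*

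**What the plan says.** The document is titled Study Protocol and dated "July 22nd, 2023". It opens with screening and enrolment checklists and closes with two statistical sections, both in the past tense.

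- **Pilot Usability Phase.** "Analyses were performed using R version 4.3.3 (R Core Team, 2024"). Three participants (1 SET, 2 AC) "were identified as outliers for all LTPAQ-SCI categories (Studentized residual > 3.0 and high leverage on predictors of interest") and were left out of all LTPAQ-SCI analyses. The section calls itself exploratory, concentrates on effect sizes with 95%, 85% and 75% intervals, and sets no alpha.
- **Feasibility Phase.** "All analyses were performed using R version 4.5.0 (R Development Core Team, 2025"). The primary outcome is change in LTPAQ-SCI, with Week 8 as primary endpoint. Five participants (3 in Arm 1, 2 in Arm 2) "had unusually high scores for mild, moderate, and total LTPA, and were identified as model outliers for these outcomes". The text continues: "Ultimately, these participants were excluded from analyses of the primary outcome due to the high likelihood of data entry errors during data collection". The mixed models are described as intent-to-treat. LTPAQ-SCI measures were square-root transformed to satisfy normality, after the data had been examined for it. The section ends: "Significance was set at $\alpha=0.05$ for all analyses".

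The text supplied contains no forward-looking outlier or transformation rule, no cut-off for high leverage, no analysis retaining the excluded participants, and no earlier dated analysis plan.

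**The concern.** A 5% false-positive rate belongs to an analysis whose participant set and scale do not depend on the results. The Feasibility section names a primary outcome and endpoint and sets a significance level, which is the usual form of a confirmatory test. It does not separate what was fixed beforehand from what was decided after looking. A person opening a document dated 2023 could take a p-value below 0.05 for LTPAQ-SCI as confirmatory when the set it was computed on was settled after the outcome values and model fit had been seen. What is at stake is the strength of the claim the trial can make on its primary outcome.

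**Working it through.** **1. Order of events.** The header date is July 2023. The software citations are 2024 (pilot) and 2025 (feasibility). The statistical text therefore postdates the header. If the header date covers only the procedures, the statistical sections carry no date in the supplied text.

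**2. Which choices used the data.**

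| Element | Pilot section | Feasibility section | Reading |
|---|---|---|---|
| Week 8 as primary endpoint | Yes | Yes | No sign of data-dependent choice |
| Mixed model, time x arm | Yes | Yes | No sign of data-dependent choice |
| Square root of LTPAQ-SCI | Yes | Yes | Possible: justified by normality, and normality was examined first |
| Exclusions | 3, outlying in all categories | 5, outlying in mild, moderate and total | Shown: needs observed scores and a fitted model |

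Both phases use the same residual threshold (3.0) plus high leverage, but the categories on which people were flagged differ, and leverage has no stated cut-off.

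**3. Share excluded.** Pilot: 3/36 = 8.3%, if the stated sample size of 36 was the number analysed. The Feasibility sample size is not given. For assumed totals, 5/60 = 8.3%, 5/100 = 5.0% and 5/200 = 2.5%.

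**4. Effect on the 5% level.** The plan has no figure to reproduce, so this is simulation under no treatment effect.

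*Assumptions.* Log score = 4 + u + e, with u ~ N(0, 0.7²) shared within a participant and e ~ N(0, 0.8²) drawn separately at baseline and Week 8. The log-scale correlation is 0.49/(0.49 + 0.64) = 0.43. A two-sample t-test of change stands in for the mixed model with bootstrap intervals. Participants are dropped if |t_i| > 3, where t_i = r_i / √[s²₍ᵢ₎(1 − h_i)] and h_i = 1/n per arm. There are 6,000 trials per row, so the Monte Carlo standard error near 5% is √(0.05 × 0.95/6,000) = 0.3 percentage points.

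| n per arm (assumed) | Square root, all kept | Square root, residuals > 3 dropped | Better of kept or dropped | Best of four (raw or square root, kept or dropped) |
|---|---|---|---|---|
| 18 | 4.6% | 6.2% | 7.5% | 9.4% |
| 30 | 4.6% | 6.2% | 7.5% | 9.6% |
| 50 | 4.8% | 6.1% | 7.9% | 10.3% |
| 100 | 4.3% | 5.8% | 7.3% | 10.1% |

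Two further simulations under other assumptions bracket these. Zero-inflated lognormal minutes with correlation 0.5 gave 7.5%, 8.7% and 9.5% for the best of four at 18, 40 and 80 per arm. Another set gave 6.6-6.8% for dropping residuals above 3 alone and about 11-12% for the best of four.

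**5. Reading the results.** Two effects are mixed together. Dropping large residuals raises the rate to about 6-7% even when the rule is fixed in advance, because trimming shrinks the error variance. Freedom to choose among the four versions takes it to roughly 8-12%.

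**The case against.** The strongest defence has four parts.

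**The text is open about what it is.** Neither section calls itself prespecified, and the past tense and reported exclusions plainly describe completed work. A reader might infer that the sponsor is presenting a post hoc analysis as a prior plan. The documents do not support that: no such claim is made, title pages were removed before review, and an earlier plan may exist elsewhere. What stands is that the section keeps a primary outcome and an alpha without saying which elements came first.

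**The pilot is a precedent.** The pilot section already has the same endpoint, transformation, residual threshold and model. A reader might infer that everything in the Feasibility analysis, including the time point, was open to choice. That goes too far. The programme lasts 8 weeks, the post-intervention packet goes out 58 days after randomisation, and both sections name Week 8. The precedent also weakens the case against the transformation. It does not settle it, because the pilot is described as an interim analysis and its data may overlap with the Feasibility data. Nor does it cover the exclusions, where the flagged categories differ between phases.

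**Removing wrong data is legitimate.** That is so if the values are shown to be wrong. Here the reason given is a high likelihood of entry error, inferred from extreme scores and model fit, with no reported check of the entries. Intent-to-treat sits awkwardly beside it.

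**The simulations rest on assumptions.** This is correct. Arm sizes, distributions and the simplified test are all assumed, and different assumptions give different figures. They should not be read as an upper bound or as evidence that any version was selected.

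One limit on scope also holds: alpha = 0.05 is stated only in the Feasibility section, so the point does not extend to the pilot.

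**Conclusion.** The point holds for the Feasibility-phase LTPAQ-SCI analysis. Data-dependent choice is shown for the five exclusions, possible for the square-root transformation, and not shown for Week 8 or the mixed model. The nominal 5% level is therefore not assured for the primary outcome. For scale, the rate is about 6-7% from dropping large residuals and roughly 8-12% if the scale and the outlier handling were both free. Both ranges depend on assumed distributions and arm sizes and on a two-sample test in place of the mixed model. Whether an earlier plan would resolve the matter cannot be judged from these documents.

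**What to change.** 1. Give the statistical section its own date and version, and describe it as a report of analyses performed.
2. Mark the five exclusions as chosen after data inspection, and the transformation too, unless an earlier dated plan contains them.
3. If an earlier plan exists, cite it and report its version of the LTPAQ-SCI analysis first.
4. If none exists, report LTPAQ-SCI with the available data of all randomised participants included, alongside the result with outliers excluded. Present both as exploratory estimates with 95% CIs and without a confirmatory significance claim. The pilot section already frames its results this way.

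The cost is some wording, one additional model run, and a less favourable claim if no earlier plan can be produced.
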